1.3.3. UNMET CLINICAL NEED

In the absence of revascularization options, most patients with CLI require amputation within 6 months. Patients requiring major amputation face a diminished quality of life, an unfavorable natural history and need extensive resources for their post-amputation rehabilitation and course. The 1-year amputation-free survival rate for patients diagnosed with CLI is 45%; the mortality rate is approximately 25% and may be as high as 45% in those who have undergone amputation.^{1,6,16} Management of this end-stage disease process consumes a significant amount of healthcare resources.^{17,18} Clearly, new therapeutic approaches are required.

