5.2. Statistical Methods

Two-sided p -values < 0.05 will be considered statistically significant, unless otherwise stated.

Separate statistical tests will be performed at each time point for key endpoints of interest.

In general, an overall test to determine if there is a statistically significant difference among the three treatment arms will be conducted first. Further comparisons will be made to determine if either the low or high dose groups are significantly different from the placebo group.

For continuous variables, a one-way analysis of variance (ANOVA) with treatment group (high dose, low dose, and placebo) as a factor will be used to determine if there is a significant difference among the groups. The low and high dose groups will each be compared against the placebo group using Dunnett's test. The mean difference between the VM202 groups versus placebo along with 95% confidence intervals for the mean difference will also be presented. To be viewed as secondary, an additional set of analyses will be run using non-parametric tests. A Jonckheere-Tepstra test will be applied to the VAS change from baseline results to detect overall trend differences. Non-parametric pairwise treatment comparisons versus placebo will also be made using Wilcoxon Rank Sum test. Within each treatment group for each endpoint, both a paired t-test (parametric) and Wilcoxon Signed Rank test will be run to test for differences comparing baseline to each post-baseline assessment.

For categorical variables, Fisher's exact test will be used to determine if there is a significant difference among the three treatment groups. Separate Fisher's exact tests will be used to compare the low and high dose groups to the placebo group.

For time-to-event variables (such as amputation, limb salvage and mortality), Kaplan-Meier estimates will be used to estimate survival times. Differences in survival times will be compared among groups using the log-rank test.

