6. ANALYSIS POPULATIONS

The following subject populations will be used for analysis:

The Intent-to-Treat (ITT) population will include all subjects who were randomized regardless of whether treatment was received. Subjects will be analyzed according to the treatment to which they were randomized.

The Safety population will include all subjects who receive at least one dose of study drug medication and data will be analyzed according to the treatment actually received. The safety analyses will be performed on the Safety population.

The per-protocol (PP) population will include all subjects who received the correct dose of study drug medication, have the 9-month VAS assessment, and do not have any protocol violations or major deviations as determined by Medical Monitoring. The per-protocol population will be determined in a blinded review before database lock. Subjects will be analyzed according to the treatment to which they were randomized. Primary efficacy analyses will be performed on the PP population.

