10.2.7. Amputation and Mortality Rate

The rates of amputation, limb salvage and mortality will be analyzed for all treated subjects per actual treatment using the method for time-to-event variables. The probability of being event-free at 6 and 12 months will be summarized for each treatment arm and compared vs. Placebo using a Log Rank test.

The duration of time to amputation will be defined as the number of days between the day of amputation – the first dose date + 1. If a subject does not report amputation, then the date that the subject will be censored at the date of study discontinuation. If the date of study discontinuation is not available, then the subject's censor date will be the last known visit the subject attended. The same calculation will be repeated for limb salvage and mortality (time to death).

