6.2.2.2	Transcutaneous Oxygen Pressure Assessment- TcPO ₂ Ratio - Posterior Calf (ITT Population)
6.2.3.1	Transcutaneous Oxygen Pressure Assessment- TcPO ₂ Ratio- Dorsum Foot (Per-Protocol Population)
6.2.3.2	Transcutaneous Oxygen Pressure Assessment- TcPO ₂ Ratio - Dorsum Foot (ITT Population)
7.1.1	Ankle Brachial-Index – Index Leg (Per-Protocol Population)
7.1.2	Ankle Brachial-Index – Index Leg (ITT Population)
7.2.1	Ankle Brachial-Index – Non-Index Leg (Per-Protocol Population)
7.2.2	Ankle Brachial-Index – Non-Index Leg (ITT Population)
8.1.1	Toe Brachial-Index – Index Leg (Per-Protocol Population)
8.1.2	Toe Brachial-Index – Index Leg (ITT Population)
8.2.1	Toe Brachial-Index – Non-Index Leg (Per-Protocol Population)
8.2.2	Toe Brachial-Index – Non-Index Leg (ITT Population)
9.1.1	Wound Area (Per-Protocol Population)
9.1.2	Wound Area (ITT Population)
9.2.1	Categorical Analysis of Wound Healing (Per-Protocol Population)
9.2.2	Categorical Analysis of Wound Healing (ITT Population)
10.1.1	VascuQoL – Activity (Per-Protocol Population)

10.1.2	VascuQoL – Activity (ITT Population)
10.2.1	VascuQoL – Symptom (Per-Protocol Population)
10.2.2	VascuQoL – Symptom (ITT Population)
10.3.1	VascuQoL – Pain (Per-Protocol Population)
10.3.2	VascuQoL – Pain (ITT Population)
10.4.1	VascuQoL – Emotional (Per-Protocol Population)
10.4.2	VascuQoL – Emotional (ITT Population)
10.5.1	VascuQoL – Social (Per-Protocol Population)
10.5.2	VascuQoL – Social (ITT Population)
10.6.1	VascuQoL – Total (Per-Protocol Population)
10.6.2	VascuQoL – Total (ITT Population)
10.7.1	VascuQoL- By Individual Question (Per-Protocol Population)
10.7.2	VascuQoL- By Individual Question (ITT Population)
11.1.1	Amputation – Event-Free Probability (Per-Protocol Population)
11.1.2	Amputation – Event-Free Probability (ITT Population)
11.2.1	Limb Salvage – Event-Free Probability (Per-Protocol Population)
11.2.2	Limb Salvage – Event-Free Probability (ITT Population)
11.3.1	Mortality – Event-Free Probability (Per-Protocol Population)
11.3.2	Mortality – Event-Free Probability (ITT Population)
12.1	Rutherford Classification of Disease Severity (Per-Protocol Population)
12.2	Rutherford Classification of Disease Severity (ITT Population)
13	Study Drug Exposure(Safety Population)
14	Treatment Emergent Adverse Events by System Organ Class and Preferred Term (Safety Population)
15	Treatment Emergent Adverse Events by Maximum Severity (Safety Population)

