APPENDIX B: TABLE LAYOUTS

Table 1
Subject Disposition
All Subjects

	Placebo	VM202- 8 mg	VM202- 16 mg
Subjects Enrolled	n (Overall)		
ITT Population ^[1]	n	n	n
Safety Population ^[2]	n (%)	n (%)	n (%)
Per-Protocol Population ^[3]	n (%)	n (%)	n (%)
Received All Planned Doses of VM202?			
Yes	n (%)	n (%)	n (%)
No	n (%)	n (%)	n (%)
Last Visit Attended			
Any Visit Prior to Visit- Day 0	n (%)	n (%)	n (%)
Visit- Day 0	n (%)	n (%)	n (%)
Visit- Day 14	n (%)	n (%)	n (%)
Visit- Day 28	n (%)	n (%)	n (%)
Visit- Day 42	n (%)	n (%)	n (%)
Visit- Day 49	n (%)	n (%)	n (%)
Visit- Day 90	n (%)	n (%)	n (%)
Visit- 6 Months	n (%)	n (%)	n (%)
Visit- 9 Months	n (%)	n (%)	n (%)
Visit- 12 Months	n (%)	n (%)	n (%)
Completed Study?			
Yes	n (%)	n (%)	n (%)
No	n (%)	n (%)	n (%)

Note: Percentages based on number of subjects in the ITT population.

[1] All subjects who were randomized regardless of whether treatment was received.

[2] All subjects who received at least one dose of study drug.

[3] All subjects who received the correct dose of study drug medication, have the 9-month VAS assessment, and do not have any protocol violations or major deviations.

path\program.sas date time

Table 1
Subject Disposition
All Subjects

	Placebo	VM202- 8 mg	VM202- 16 mg
Primary Reason for Discontinuation			
Screen failure	n (%)	n (%)	n (%)
Lost to Follow-up	n (%)	n (%)	n (%)
Adverse Event	n (%)	n (%)	n (%)
Non-compliance	n (%)	n (%)	n (%)
Subject withdrew consent	n (%)	n (%)	n (%)
Principal Investigator decision	n (%)	n (%)	n (%)
Subject requires intervention for treatment of acute limb ischemia	n (%)	n (%)	n (%)
Death	n (%)	n (%)	n (%)
Other	n (%)	n (%)	n (%)

Note: Percentages based on number of subjects in the ITT population.

[1] All subjects who were randomized regardless of whether treatment was received.

[2] All subjects who received at least one dose of study drug.

[3] All subjects who received the correct dose of study drug medication, have the 9-month VAS assessment, and do not have any protocol violations or major deviations.

path\t_program.sas date time

Table 2.1
Demographic and Baseline Characteristics
ITT Population

	Placebo (N=)	VM202- 8 mg (N=)	VM202- 16 mg (N=)	p-value
Age (years) ^[1]				
N	n	n	n	
Mean (SD)	xx.x (xx.xx)	xx.x (xx.xx)	xx.x (xx.xx)	x.XXXX ^[2]
Median	xx.x	xx.x	xx.x	
Min, Max	xx, xx	xx, xx	xx, xx	
Sex				x.XXXX ^[3]
Male	n (%)	n (%)	n (%)	
Female	n (%)	n (%)	n (%)	
Race				x.XXXX ^[3]
Caucasian	n (%)	n (%)	n (%)	

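### The Kaplan-Meier amputation and limb-salvage probabilities count death as ordinary censoring, and the per-protocol event tables leave out subjects who died before Month 9

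*SAP*

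**What the plan says.** SAP 5.2 names amputation, limb salvage and mortality as time-to-event variables. For these, "Kaplan-Meier estimates will be used to estimate survival times", and "Differences in survival times will be compared among groups using the log-rank test". SAP 10.2.7 asks for the event-free probability at 6 and 12 months by arm. For a subject with no amputation, "the subject will be censored at the date of study discontinuation"; if that date is missing, the "censor date will be the last known visit the subject attended". The same calculation is repeated for limb salvage and for death. No separate rule covers a death without amputation. The Table 1 layout in SAP Appendix B has Death as a row under "Primary Reason for Discontinuation".

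Protocol 6.2.2 lists the major amputation rate, and mortality, at six and twelve months as secondary endpoints. Protocol 1.3.3 gives background for the disease: "The 1-year amputation-free survival rate for patients diagnosed with CLI is 45%; the mortality rate is approximately 25" per cent. It adds that mortality may reach 45% after amputation.

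The analysis population is stated in three ways:
- SAP 10.2.7 takes every treated subject, by treatment actually received.
- SAP 10.2 puts the secondary efficacy analyses in the per-protocol (PP) and ITT populations, and Appendix A follows it: the titles of Tables 11.1.1, 11.2.1 and 11.3.1 contain "Event-Free Probability (Per-Protocol Population".
- Figure 1 in Appendix C is headed Safety Population.

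SAP 6 requires PP subjects to "have the 9-month VAS assessment".

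**The concern.** A subject who dies with the limb intact can no longer lose it. If the death is treated as ordinary censoring, Kaplan-Meier redistributes that subject's probability to those still at risk, as though the limb could still be lost later. The result is the amputation risk in a hypothetical population without deaths. The secondary endpoint is the rate in these patients, and 1−KM can only equal or exceed it. The time-to-death curve is not affected.

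A second problem concerns the PP tables and does not depend on any mortality assumption. Membership is decided by being alive and assessed at Month 9, yet the tables report events from first dose onward. Early deaths, and amputees who died or left before Month 9, are removed before the estimate is made. At stake are the 6- and 12-month probabilities that would be reported from this study and carried into later planning.

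**Working it through.** The plan gives no rate, event count or power for amputation, so there is no figure of its own to reproduce. The check below estimates how large the excess could be.

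**Inputs.** One-year amputation-free survival is 45%, so 55% are amputated or dead; total one-year mortality is 25%; mortality after amputation is up to 45% (all Protocol 1.3.3). Arm sizes are 20:20:10 (SAP 4). Assumption: constant cause-specific hazards, *a* for amputation and *d* for death without amputation.

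**Splitting the 55%.** Only deaths before amputation compete. Let A be the proportion amputated first, D the proportion dying first, and *m* the one-year mortality among amputees. Then A + D = 0.55 and D + *m*A = 0.25, so A = 0.30/(1 − *m*).

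**Formulas.**
- *a* + *d* = −ln(0.45) = 0.7985 per year, and *a* = 0.7985 × A/0.55.
- True cumulative incidence at time *t* = *a*/(*a* + *d*) × [1 − exp(−(*a* + *d*)*t*)].
- Planned quantity: 1−KM = 1 − exp(−*at*).

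**At 12 months.**

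| *m* | D | A | *a* | True incidence | 1−KM | Excess (points) |
|---|---|---|---|---|---|---|
| 0 (all deaths precede amputation) | 25% | 30% | 0.4355 | 30.0% | 35.3% | 5.3 |
| 25% | 15% | 40% | 0.5807 | 40.0% | 44.1% | 4.1 |
| 45% | 0.5% | 54.5% | 0.7919 | 54.5% | 54.7% | 0.2 |

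**At 6 months, upper case.** True incidence is (30/55) × [1 − exp(−0.3993)] = 18.0%; 1−KM is 1 − exp(−0.2178) = 19.6%. The excess is 1.6 points.

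**Timing.** If hazards are not constant, the upper case gives a 12-month 1−KM between 30% (all deaths after the last amputation) and 30/75 = 40% (all deaths before the first), for a true 30%.

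**Sampling error.** In 20,000 simulated arms of the upper case, mean 1−KM against mean incidence was 35.4% against 30.1% with 10 subjects and 35.2% against 29.9% with 20. The standard deviation of 1−KM was 17 and 12 points.

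**Effect of mortality.** Hold *a* at 0.4355 and double *d* from 0.363 to 0.726. 1−KM stays at 35.3%. Cumulative incidence falls from 30.0% to (0.4355/1.1615) × [1 − exp(−1.1615)] = 25.8%.

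**PP tables.** The 9-month visit has a window of one month either side, so its earliest in-window date is Month 8. A subject who dies by Month 6 has no 9-month VAS and is not in the PP set. Table 11.3.1 must therefore show essentially 0% six-month mortality in every arm, whatever happens in the trial.

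**The case against.** The strongest objection is that the analysis is a recognised one and the comparison between arms is sound. That stands: with deaths censored, the log-rank test compares cause-specific amputation hazards. A reader might infer that Kaplan-Meier lets an arm look better or worse on amputation because of its mortality. The calculation does not support this. At a fixed amputation hazard, 1−KM does not move with mortality; cumulative incidence does. The fault is confined to the absolute probabilities and curves.

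A reader might also infer that the protocol expects 25% one-year mortality in this trial. It does not say so. The figure is background on diagnosed patients, and Protocol 3.3.2 excludes life expectancy under 6 months, NYHA class III or IV, unstable angina, and stroke or infarction within 3 months. Protocol 1.3.3 also says that most patients without revascularization options need amputation within six months. Amputations that early would leave fewer deaths to precede them and push the excess toward the low end. The 5.3 points is an upper case under constant hazards, and sampling error exceeds it.

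Table 11.1.1 also shows the crude number and percentage amputated, which with otherwise complete follow-up is close to the overall incidence. That helps a careful reader, but it gives no 6-month figure, does not handle dropout, and leaves the Kaplan-Meier probabilities as they are. Mortality has its own tables, and the SAP never calls the amputation curve amputation-free survival.

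Finally, ITT tables and Safety figures are already planned. They do not repair the PP tables.

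**Conclusion.** Two separate points hold.

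First, the planned 6- and 12-month amputation and limb-salvage probabilities do not estimate incidence, and 1−KM is biased upward. That deaths are censored follows from the discontinuation rule together with Table 1; the SAP does not say it outright. For amputation, the 12-month excess is 0.2 to 5.3 points, depending on how many deaths precede amputation. The range rests on background rates and constant hazards. The bias is modest beside the noise in arms of 10 to 20, but it is systematic and avoidable in a study that SAP 4 describes as sized to inform a pivotal trial. The planned log-rank comparison is not wrong.

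Second, the PP versions of Tables 11.1 to 11.3 select on survival to Month 9 and contradict the treated-subject population in SAP 10.2.7. Six-month mortality in Table 11.3.1 carries no information. This needs no assumption about rates.

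The change should be made before database lock.

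**What to change.** - In SAP 10.2.7 and Tables 11.1.x and 11.2.x, report cumulative incidence at 6 and 12 months with death as a competing event. State explicitly how a death without the event is handled.
- Keep the log-rank test and label it a comparison of cause-specific hazards.
- Show mortality by arm alongside, because cumulative incidence falls when mortality rises and should not be read alone.
- Amputation-free survival may be added as a descriptive supplement. It is not a protocol endpoint, so it needs no further test.
- Drop the PP versions of Tables 11.1 to 11.3, and exempt these endpoints from the PP and ITT instruction in SAP 10.2.
- Make the treated (Safety) population, by actual treatment, the main set for these tables. Keep ITT as a supplement. Because SAP 10.2.7 counts from first dose, use randomization as the time origin for subjects never treated.

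The dates needed are already listed: procedures in Listing 39 and deaths in Listing 40. The cost is revised SAP wording, a little more programming and a changed table list.

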10.2.8. Rutherford Classification

The Rutherford Classification measurement (which characterizes peripheral arterial disease severity using a discrete 7 point scale from 0-6) and change from baseline will be summarized at each visit by treatment arm using method for continuous variables.

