10.2.8.1 Imputation Methods of Rutherford Results for the ITT Population

For subjects without the efficacy endpoint (Rutherford Classification change from baseline to any post baseline result), the following imputation methods will be applied:

- For missing Baseline Rutherford Classification, assign the Rutherford Classification score at Screening if the Rutherford Classification score score at Day 0 is missing.
- For any post baseline Rutherford Classification, assign the post baseline Rutherford Classification score prior to the missing post baseline Rutherford Classification via the last observation carried forward (LOCF) method.

For subjects who had a major amputation or limb procedure carried out, the following imputation methods will be applied:

- For subjects with a major amputation, assign the Rutherford Classification score prior to the amputation.

- For subjects with a limb salvage, assign the Rutherford Classification score prior to the intervention.

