Programmer note sort by assessment date within each subject.

Listing 26
Rutherford Classification

Treatment Group	Subject ID	Visit	Date of Assessment (Study Day)	Rutherford Classification	Comments
Placebo	xxxxxx	visit	date9. (xx)		
		visit	date9. (xx)	x	comments
				...	comments
VM202- 8 mg	xxxxxx	visit	date9. (xx)	x	comments
		visit	date9. (xx)	x	comments
				...	comments
VM202- 16 mg	xxxxxx	visit	date9. (xx)	x	comments
		visit	date9. (xx)	x	comments
				...	comments

Note: Scale for Rutherford Classification-

0= Asymptomatic - No hemodynamically
1= Mild Claudication
2= Moderate Claudication
3= Severe Claudication
4= Ischemic Rest Pain

5= Minor Tissue Loss - Non-healing ulcer, focal gangrene with diffuse pedal ischemia

6= Major Tissue Loss - Extending above the TM level, functional foot no longer salvageable

Note: Study Day = [(Date of Event) - (Treatment Start Date)]; 1 is added to the difference when 'Date of Event' is greater than or equal to 'Treatment Start Date'.
path\t_program.sas date time

Programmer note sort by date of assessment within each subject

Listing 27
Study Drug Administration

Treatment Group	Subject ID	Visit Date (Study Day)	Was a Dose Administered?	Study Leg Assignment	Kit #	Start Time of First Injection	Stop Time of Last Injection	Was Total Volume (8mL) Administered?	Reason Total Volume Not Administered	Total Volume Administered (mL)	Injection Zones
						If No,					
Placebo	xxxx	Date9.	Yes/No	left/right	xxxx	time5.	time5.	Yes/No	xxxxxx	xx	I/II/II/IV
	xxxx	Date9.	Yes/No	left/right	xxxx	time5.	time5.	Yes/No	xxxxxx	xx	I/II/II/IV
VM202- 8 mg	xxxx	Date9.	Yes/No	left/right	xxxx	time5.	time5.	Yes/No	xxxxxx	xx	I/II/II/IV
	xxxx	Date9.	Yes/No	left/right	xxxx	time5.	time5.	Yes/No	xxxxxx	xx	I/II/II/IV
VM202- 16 mg	xxxx	Date9.	Yes/No	left/right	xxxx	time5.	time5.	Yes/No	xxxxxx	xx	I/II/II/IV
	xxxx	Date9.	Yes/No	left/right	xxxx	time5.	time5.	Yes/No	xxxxxx	xx	I/II/II/IV
...											

Note: Study Day = [(Date of Event) - (Treatment Start Date)]; 1 is added to the difference when 'Date of Event' is greater than or equal to 'Treatment Start Date'.
path\t_program.sas date time

Programmer note sort by visit date within each subject

Listing 28
Adverse Events

Treatment Group	Subject ID	AE #	Adverse Event// Preferred Term	Start Date (Study Day)	End Date (Study Day)	Severity	Treatment	Study Drug Action	Relationship To Study Drug	Relationship To Procedure	Relationship To Underlying Disease	Outcome	Serious?

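### In the ITT Rutherford analysis a major amputation never worsens the score, because the class from before the amputation is carried forward

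*SAP*

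**What the plan says.** SAP 10.2.8 treats the seven-point Rutherford scale as a number: class and change are summarised by visit and arm "using method for continuous variables". SAP 5.2 says what that method is: "For continuous variables, a one-way analysis of variance (ANOVA) with treatment group (high dose, low dose, and placebo) as a factor", with Dunnett comparisons against placebo and paired t-tests within arms. Rank tests are also planned: "To be viewed as secondary, an additional set of analyses will be run using non-parametric tests". The Table 12.1 layout contains both sets, and Table 12.2 repeats it for ITT.

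SAP 10.2.8.1 is headed "Imputation Methods of Rutherford Results for the ITT Population". One bullet reads: "For subjects with a major amputation, assign the Rutherford Classification score prior to the amputation". It stands apart from the missing-data bullets and, as written, is not limited to visits where a class is missing. Unlike the corresponding VAS rule in SAP 10.1.2, it does not ask for a post-baseline score, so the baseline class can be the value carried.

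The scale note to Listing 26 (SAP Appendix D) gives the worst category as "6= Major Tissue Loss - Extending above the TM level, functional foot no longer salvageable".

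**The concern.** Rutherford class is a limb-severity scale, and losing the limb is the worst limb outcome. Under the carry-forward rule that event adds nothing to the score. A subject who improves by a class at month 6 and then loses the leg is still counted as improved at months 9 and 12. An arm with more amputations would look no worse in Table 12.2, and an arm in which amputations were prevented would get no credit there. The rank tests do not help, because they use the same carried values.

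The protocol takes a different view of limb loss elsewhere. Section 4.2.10 gives a TcPO₂ site lost to amputation a value of zero, the worst possible.

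**Working it through.** The documents give no power, expected effect or amputation rate by arm for Rutherford class, so there is no figure of the plan to reproduce.

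**Inputs from the documents**
- Entry class 4 or 5 (Protocol 3.3.1, inclusion 2).
- Post-baseline classification at 6, 9 and 12 months (Protocol synopsis, 3.4.12 to 3.4.14 and Appendix 1; SAP Table 12.1 programmer note). SAP Table 2 may carry a further mark near Day 90, but its column alignment is uncertain in the copy read. If that visit were real, step 1 would hold for amputations before Day 90.
- Planned arm sizes 20, 20 and 10 (Protocol synopsis; SAP 4).
- Class 6 as the worst category (SAP Listing 26).

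**Assumptions**
- A major amputation of the treated leg belongs in class 6.
- Amputation rates lie between 0% and 30% per arm. Protocol 1.3.3 gives 45% one-year amputation-free survival and about 25% mortality for CLI in general; 100 − 45 − 25 = 30 is a rough upper anchor.

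**Step 1: score under the rule.** If the amputation precedes month 6, the only earlier class is baseline, so change = baseline − baseline = 0. If it comes later, the change is the one at the last visit before the amputation: better, unchanged or worse. The amputation itself always adds 0.

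**Step 2: error per amputee.** Error = 6 − carried class. Carried class 4 gives 2 and class 5 gives 1. After improvement to class 3 it is 3; if the subject is already class 6 it is 0.

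**Step 3: shift in an arm mean per amputee carried at 4 or 5.** Shift = (6 − carried class)/n.
- Placebo, n=10: 1/10 = 0.10 to 2/10 = 0.20.
- Active arm, n=20: 1/20 = 0.05 to 2/20 = 0.10.

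**Step 4: shift in the contrast.** Active minus placebo contribution of amputees, with class 6 scoring and amputation before month 6 = (6 − baseline class) × (active rate − placebo rate). Under the SAP rule this contribution is 0.
- Placebo 3/10, active 2/20: 1 × (0.10 − 0.30) = −0.20 to 2 × (0.10 − 0.30) = −0.40. A benefit is hidden.
- Placebo 1/10, active 6/20: 1 × (0.30 − 0.10) = +0.20 to 2 × (0.30 − 0.10) = +0.40. Harm is hidden.
- Placebo 3/10, active 6/20: 0 at a common baseline class.

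**Step 5: simulation.** 4,000 trials of 20:20:10; baseline 4 or 5 with equal chance; non-amputees in every arm change by −1, 0 or +1 with probability 0.3, 0.6 and 0.1; all amputations before month 6; one-way ANOVA at 5%.

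| Amputated, placebo / each active arm | High dose − placebo: SAP rule | Class 6 | ANOVA rejects: SAP rule | Class 6 |
|---|---|---|---|---|
| 30% / 10% | −0.04 | −0.35 | 5% | 18% |
| 30% / 0% | −0.06 | −0.51 | 5% | 42% |
| 10% / 30% | +0.04 | +0.34 | 6% | 12% |
| 30% / 30% | 0.00 | 0.00 | 4% | 5% |

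In the first row the two rules differ by 0.35 − 0.04 = 0.31 class, inside the 0.2 to 0.4 of step 4. The small residual under the SAP rule arises because amputees score 0 while non-amputees average −0.3 + 0.1 = −0.2.

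**The case against.** The case for leaving the rule alone has real content.

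- *Limb loss is reported elsewhere.* SAP 10.2.7 analyses amputation by Kaplan-Meier and log-rank in all treated subjects, and major amputation is a protocol secondary endpoint (6.2.2). A reader might infer that amputations vanish from the results. They do not. This stands, and it confines the defect to one analysis, but it does not correct Table 12.2.
- *The rule is for ITT only.* A reader might infer that every Rutherford analysis is affected. The heading of 10.2.8.1 does not support that; for the per-protocol analysis the SAP simply states no Rutherford rule for amputees. Rutherford class is also absent from the protocol's list of secondary endpoints, although the SAP places it under secondary efficacy.
- *It is a consistent choice.* The SAP carries the pre-amputation value forward for VAS, TcPO₂, ABI/TBI and VascuQoL too, and no passage says how to classify an amputated leg. Placing it in class 6 is therefore an inference. It is a short one, since a leg lost to major amputation has no foot left to save. Consistency across endpoints does not make no change a sound severity score.
- *Arm means are not contrasts.* At 20% to 30% amputated, an arm mean is understated by 0.20 × 1 = 0.2 to 0.30 × 2 = 0.6 class. It is tempting to read that as bias in the treatment effect, or as bias favouring VM202. Neither follows: the contrast depends on the difference in rates, and the direction can go either way. Exclusion 2, which removes subjects expected to need amputation within 4 weeks, may also lower the rates.
- *Rank tests as the main analysis.* The scale is ordinal, so this is a natural suggestion, but those tests are already planned and inherit the same imputed values. Reordering them would not touch the problem.

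**Conclusion.** The concern holds in a limited form. In the ITT Rutherford analysis a major amputation cannot worsen the score, although the SAP's own scale has a category for an unsalvageable foot. Each amputee carried at class 4 or 5 is scored one to two classes too low, more after earlier improvement and not at all if already class 6.

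The part of the treatment contrast that comes from amputations is pulled toward zero. It shifts by 0.2 to 0.4 class if 30% of one arm and 10% of the other are amputated, and by little or nothing if rates and carried classes are similar. Those rates are assumed, and the sizes also rest on amputation before month 6 and on class 6 being the right category. The rule can mask benefit as easily as harm. The primary endpoint and the time-to-event analysis of amputation are unaffected by this bullet.

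**What to change.** In SAP 10.2.8.1, replace the major-amputation bullet with: assign class 6 at all visits from the date of a major amputation of the treated leg. Keep the current carry-forward rule as a sensitivity analysis of Table 12.2.

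No new data are needed. SAP 10.2.7 already requires the amputation date, Listing 39 holds procedure date and leg, and Listing 27 holds the study leg. The text should also say which amputations count as major. The cost is a short text change, one extra run of the table, and a less favourable mean in any arm with amputations. The change concerns endpoint scoring only and leaves the limb-salvage bullet and the per-protocol analysis as they are.
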